1. Physical activity behaviour

We are interested in finding out about the kinds of physical activities that people do as part of their everyday lives. The questions will ask you about the time you spent being physically active in the last 7 days. Please answer each question even if you do not consider yourself to be an active person. Please think about the activities you do at campus, such as, to get from place to place, and in your spare time for recreation, exercise or sport.

Think about all the vigorous activities that you did in the last 7 days. Vigorous physical activities refer to activities that take hard physical effort and make you breathe much harder than normal. Think only about those physical activities that you did for at least 10 minutes at a time.

(1). During the last 7 days, on how many days did you do vigorous physical activities like heavy lifting, digging, aerobics, or fast bicycling?

_____ days

No vigorous physical activities

(2). How much time did you usually spend doing vigorous physical activities on one of those days?

_____ hours per day

_____ minutes per day

Think about all the moderate activities that you did in the last 7 days. Moderate activities refer to activities that take moderate physical effort and make you breathe somewhat harder than normal. Think only about those physical activities that you did for at least 10 minutes at a time.

(1). During the last 7 days, on how many days did you do moderate physical activities like carrying light loads, bicycling at a regular pace, or doubles tennis? Do not include walking.

_____ days

No moderate physical activities

(2). How much time did you usually spend doing moderate physical activities on one of those days?

_____ hours per day

_____ minutes per day

Think about the time you spent walking in the last 7 days. This includes at work and at home, walking to travel from place to place, and any other walking that you have done solely for recreation, sport, exercise, or leisure.

(1). During the last 7 days, on how many days did you walk for at least 10 minutes at a time?

_____ days

No walking

(2). How much time did you usually spend walking on one of those days?

_____ hours per day

_____ minutes per day

Which intentions do you have for the near future?

I intent to do for at least 20 minutes a day on minimum 2 days a week (or at least 40 minutes a week)...

		not true			exactly true
1.	... perform strenuous physical activity (heart beats faster, sweating)	 ₁	 ₂	 ₃	 ₄
2.	... be moderately physically active (not fatiguing, mild sweating)	 ₁	 ₂	 ₃	 ₄
3.	... be mildly physically active (hardly strenuous, no sweating)	 ₁	 ₂	 ₃	 ₄

3. Plans of physical activity

For the next month I already planned in detail ...

		Totally disagree			Totally agree	
1.	... which concrete physical activity I will pursue (e.g. walking).	 ₁	 ₂	 ₃	 ₄	 ₅
2.	... where I will be physically active (e.g. in the park).	 ₁	 ₂	 ₃	 ₄	 ₅
3.	... on which days I will be physically active (e.g. every Tuesday and Friday).	 ₁	 ₂	 ₃	 ₄	 ₅
4.	... when I have to be especially cautious not to stop being active.	 ₁	 ₂	 ₃	 ₄	 ₅
5.	... what I can do in difficult situations, in order to remain true to my own resolutions	 ₁	 ₂	 ₃	 ₄	 ₅
6.	...how I can stay active, even if something happened	 ₁	 ₂	 ₃	 ₄	 ₅

4. Perceived Social Support of physical activity

		not true			exactly true
1.	My partner supports me to stay physically active	 ₁	 ₂	 ₃	 ₄
2.	People from my family supports me to stay physically active	 ₁	 ₂	 ₃	 ₄
3.	People like my friends helps me to stay physically active	 ₁	 ₂	 ₃	 ₄

5. Self-efficacy of physical activity

The followed questions will ask about your confidence in PA

I feel certain that I can again be physically active a minimum of 5 days a week for 30 minutes:		Totally disagree			Totally agree	
1.	... even if it is difficult.	 ₁	 ₂	 ₃	 ₄	 ₅
I feel certain that I can be physically active permanently a minimum of 5 days a week for 30 minutes:		Totally disagree			Totally agree	
2.	... even if it takes a lot of time till I am used to it.	 ₁	 ₂	 ₃	 ₄	 ₅
3.	... even if I have worries and problems (e.g. schedule difficulties).	 ₁	 ₂	 ₃	 ₄	 ₅
I feel certain that I can again be physically active a minimum of 5 days a week for 30 minutes:		Totally disagree			Totally agree	
4.	... even if I changed my concrete plans several times.	 ₁	 ₂	 ₃	 ₄	 ₅
5.	... even if I skipped a few times.	 ₁	 ₂	 ₃	 ₄	 ₅

Part II Fruit and Vegetable Intake(FVI) Behaviour and Relevant Factors

1. FVI behaviour

During the last 7 days, how many portions of fruit and vegetable have you eaten in average per day?

(1) Raw vegetables

(0, 0.5, 1, 1.5, 2, 2.5, 3, 3.5, 4, 4.5, 5 or above)

Example for one portion of raw vegetable

(2) Fruits

(0, 0.5, 1, 1.5, 2, 2.5, 3, 3.5, 4, 4.5, 5 or above)

"One portion of fruit" is equal to:

- Two small size fruits (e.g., actinidia, plum)
- One medium size fruit (e.g., orange, apple, banana)
- Half of big size fruit (e.g., Pomelo)
- A handful of other kinds of fruits (e.g., grape, strawberry). See the picture below.

(3) Fruit/Vegetable Juice

(0, 0.5, 1, 1.5, 2, 2.5, 3, 3.5, 4, 4.5, 5 or above)

Examples for one cup/portion of juice

(4) Cooked or steamed vegetables

(0, 0.5, 1, 1.5, 2, 2.5, 3, 3.5, 4, 4.5, 5 or above)

Examples for one portion of cooked or steamed vegetable

2. Intention of FVI behaviour

Which intentions do you have for the near future? I seriously intent to, ...

	not true			exactly true
1. ... eat at least 5 portions of fruit and vegetable daily .	 ₁	 ₂	 ₃	 ₄
2. ... eat fruit and vegetable at every meal.	 ₁	 ₂	 ₃	 ₄
3. ... drinking each day at least one glass of fruit- or vegetable juice	 ₁	 ₂	 ₃	 ₄

3. Plans of FVI behaviour

For the next month I already planned in detail, ...

	Totally disagree				Totally agree
1. ... what I will eat (e.g. cereals, fruits).	 ₁	 ₂	 ₃	 ₄	 ₅
2. ... at which meals I will eat fruits and vegetables (e.g. additional salad).	 ₁	 ₂	 ₃	 ₄	 ₅
3. ... how I will prepare the food.	 ₁	 ₂	 ₃	 ₄	 ₅
4. ... when I have to pay attention not to fall into old eating habits	 ₁	 ₂	 ₃	 ₄	 ₅
5. ... what I can do in difficult situations, in order to remain true to my own resolutions	 ₁	 ₂	 ₃	 ₄	 ₅
6. ...how I can eat healthy, even if something happened	 ₁	 ₂	 ₃	 ₄	 ₅

4. Perceived social support of FVI behaviour

How do you perceive your environment?

	not true			exactly true
1. My partner supports me to eat healthy	 ₁	 ₂	 ₃	 ₄
2. People from my family supports me to eat healthy	 ₁	 ₂	 ₃	 ₄
3. People like my friends help me to eat healthy	 ₁	 ₂	 ₃	 ₄

5. Self-efficacy of FVI behaviour

I feel certain that I can eat at least 5 portions of fruit and vegetable a day:	Totally disagree				Totally agree
1. ... even if it is difficult.	 ₁	 ₂	 ₃	 ₄	 ₅
I feel certain that I can permanently eat 5 portions of fruit and vegetable a day:	Totally disagree				Totally agree
2. ... even if it takes a lot of time till I am used to it.	 ₁	 ₂	 ₃	 ₄	 ₅
3. ... even if I have worries and problems (e.g. schedule difficulties).	 ₁	 ₂	 ₃	 ₄	 ₅
I feel certain that I can again eat 5 portions of fruit and vegetable a day:	Totally disagree				Totally agree
4. ... even if I changed my concrete plans several times.	 ₁	 ₂	 ₃	 ₄	 ₅
5. ... even if I skipped a few times.	 ₁	 ₂	 ₃	 ₄	 ₅

1. WHOQOL-BREF (general quality of life + physical domain)

	Very poor				Very good
(1) How would you rate your quality of life?	 ₁	 ₂	 ₃	 ₄	 ₅
The following questions ask about how much you have experienced certain things in the last four weeks.	Not at all				An extreme amount
(2) To what extent do you feel that physical pain prevents you from doing what you need to do?	 ₁	 ₂	 ₃	 ₄	 ₅
(3) How much do you need any medical treatment to function in your daily life?	 ₁	 ₂	 ₃	 ₄	 ₅
The following question asks about how completely you experience or were able to do certain things in the last four weeks.	Not at all				An extreme amount
(4) Do you have enough energy for everyday life?	 ₁	 ₂	 ₃	 ₄	 ₅
	Very poor				Very good
(5) How well are you able to get around?	 ₁	 ₂	 ₃	 ₄	 ₅
	Very dissatisfied				Very satisfied
(6) How satisfied are you with your sleep?	 ₁	 ₂	 ₃	 ₄	 ₅
(7) How satisfied are you with your ability to perform your daily living activities?	 ₁	 ₂	 ₃	 ₄	 ₅
(8) How satisfied are you with your capacity to work?	 ₁	 ₂	 ₃	 ₄	 ₅

2. Depression CES-D 10

For each of the following statements, please check the box that best describes how often you felt or behaved this way during the past week

	Rarely or none of the time (less than one day)	Some or a little of the time (1-2 days)	Occasionally or moderate amount of the time (3-4 days)	Most or all of the time (5-7 days)
1. I was bothered by things that usually don't bother me	 ₁	 ₂	 ₃	 ₄
2. I had trouble keeping my mind on what I was doing	 ₁	 ₂	 ₃	 ₄
3. I felt depressed	 ₁	 ₂	 ₃	 ₄
4. I felt that everything I did was an effort	 ₁	 ₂	 ₃	 ₄
5. I felt hopeful about the future	 ₁	 ₂	 ₃	 ₄
6. I felt fearful	 ₁	 ₂	 ₃	 ₄

7.	My sleep was restless	 ₁	 ₂	 ₃	 ₄
8.	I felt happy	 ₁	 ₂	 ₃	 ₄
9.	I felt lonely	 ₁	 ₂	 ₃	 ₄
10.	I could not get "going"	 ₁	 ₂	 ₃	 ₄

Part IV Demographic factors

1. Name: _____
2. Please indicate your sex: male/female
3. How old are you? _____
4. Your mobile phone No.: _____
5. Which of the following heart diseases have been treated during rehabilitation? (Please indicate)
 - Acute Coronary Syndrome (ACS)
 - Myocardial infarction
 - Angina Pectoris
 - Coronary infarction
 - Bypass
 - balloon dilatation (percutaneous transluminal coronary angioplasties)
 - Others: _____
6. Where do you live currently (city/ district)? _____
7. Please indicate your marital status
 - Single
 - Close relationship, not living together
 - Close relationship, living together
 - Marital partnership/Common law marriage
 - Divorced
 - Widowed
8. Please indicate if you have children
 - Yes
 - No
 If yes, how many? _____
9. Please indicate your highest school graduation
 - I do not have any school graduation (yet)
 - Primary school graduation
 - Secondary school graduation
 - High school graduation
 - Junior college graduation
 - University graduation or above
 - Other: _____
10. Please indicate your current work status
 - Employed, fulltime
 - Employed, part-time
 - In training
 - Unemployed/searching job
 - In pension

- Housewife/Househusband
- Other: _____

11. Please indicate if you already returned to work

- Yes
- No

If yes, how many weeks have passed since rehabilitation until you returned to work? _____
weeks

Other:

Your body height is: _____ cm

Your body weight is: _____ kg

7. Expected duration : 16 months (max 24 months)

Proposed starting date: 1 Jul 2018

Expected completion date: 31 Oct 2019

8. Estimated cost of the whole project (in Hong Kong dollars):

(Please also observe the Panel Houserules while preparing the budget:

http://gs.hkbu.edu.hk/en/home/download/for_staff/)

(Panels can at their discretion fund exceptionally high quality Category II proposals up to a funding limit of HK\$180,000. For budget request that is greater than \$150,000, please project justifications under 9(d) below.)

				Year 1	Year 2	Total
(a)	Staff*	Salary	No. of			
	Rank	per month	Months			
	Research Assistant X 1	\$12,960	4.0	\$51,840.0	\$0.0	\$51,840.0
(b)	Equipment (please itemise and include cost of computing equipment in the budget total)					
(c)	General Expenses** (please itemise)					
	(1) Website set-up			\$65,000	\$0	
	(2) Participant fee			\$10,790	\$0	
	(3) Promotion materials			\$280	\$0	
	(4) Transportation and accommodation expenses			\$2,920	\$0	
	(5) Nurse helper			\$9,170	\$0	
						\$88,160
(d)	Conference / Publication** (see Note)					
	Health and exercise psychology related confere			\$10,000	\$0	\$10,000

Total***:	\$150,000.0	\$0.0	\$150,000.0

* FRG normally supports research support staff at the Research Assistant level.

** PI should include the cost for the medical surveillance programme for research personnel that would involve the use of organophosphate and 2,3,7-8 TCDD as well as other highly toxic chemicals suggested by the Laboratory Safety Sub-Committee. For programme details, please contact the EHSU of the Estates Office.

*** Should there any other research funds that have already been obtained for this project, such amount will be deducted from the total cost of the FRG (Item 10-11 refers).

Note: With effect from the 2011/2012 academic year, FRG supports conference and publication charges up to \$10,000 for PI to attend recognized international conference and to disseminate the research results.

9. (a) Justifications for each category/item of the budget in Item 8 above:

(Regarding 8(a), list the duties and time involved for the research support staff required. Also list the division of work / duties between the PI and the research support staff).

Staff Cost:

A full-time research assistant will be employed for 4 months. S/he will assist website set-up and function test, main study implementation, data management and analysis, and report writing.

Equipment Cost:

Nil.

General Expenses:

(1) An e-health learning website will be set up by an IT production company in Shenzhen, China. In addition, the SMS group message service will be included in this website platform.

(2) Participants will be rewarded HK\$65 (RMB50) cash if they complete all data collection at three time measurement points.

(3) For participant recruitment, flyer will be made and distributed to patients at hospital. The content of flyer will introduce the e-health program.

(4) PI will visit hospital for study promotion twice in total. The transportation fee will be 500 (round trip) HKD x 2 = 1,000 HKD; the accommodation fee will be 480HKD x 2 (nights) x 2 = 1,920 HKD.

(5) After communicated with the director of cardiac rehabilitation center who is also the co-investigator of this project, a nurse helper in Guangdong General Hospital will be employed

for 7 months in this study with in total payment of HK\$9,170 (7 months x HK\$ 1310/month). She will assist with recruitment of patients in hospital, and motivate patients to attend the weekly intervention session and complete online questionnaire survey.

Conference and Publication Cost :

This research topic is very popular in the field of health promotion. The investigators would like to attend an international conference to disseminate the research results. In addition, for publishing a journal paper, language editing fee or publication fee will be chargeable.

9. (b)(i). Declaration on the Equipment Procurement:

- I declare that no equipment is required; OR
- I declare that the equipment indicated in 8(b) above is not available in the department/faculty; OR
- I declare that all or some of the equipment (please provide details in the following text box) indicated in 8(b) above is available in the department/faculty but cannot be used by me in view of the following reasons (max 500 words):

9. (b)(ii). Declaration on the Equipment Procurement:

- I declare that no research-related software licence / dataset is required; OR
- I declare that the research-related software licence / dataset indicated in 8(c) above is not available in the department/faculty; OR
- I declare that all or some of the research-related software licence / dataset (please provide details in the following text box) indicated in 8(c) above is available in the department/faculty but cannot be used by me in view of the following reasons (max 500 words):

9. (c) Facilities and major equipment already available in addition to those requested in Item 8(b)

A work station, with a computer set will be provided to Research Assistant. No extra equipment will be needed in this project.

9. (d) Justifications for requesting budget greater than \$150,000 for exceptionally high quality Category II proposals (up to a funding limit of \$180,000)

Nil.

10. Other research funds that have already been obtained from other sources for this project (if any):

(Please give source(s) of funding and amount. This amount will be deducted from the total cost of the project in Item 8 above)

(Please give source(s) of funding and amount.)

11. Allocation for Faculty Research Grant Requested:

(Item 11 = Item 8 - Item 10)

\$ 150,000

12. Have funds been sought previously for the same or similar project(s)? If so, please state:

Organisation/ Committee applied to:	
Project Code:	
Project Title: (if different from item 1 above)	
Date of Application:	
Outcome:	

NOTE: If this proposal is similar to a proposal that has been submitted to the RC (including previous round of FRG)/RGC or other funding bodies, please revisit the main concerns/suggestions previously expressed by the internal and/or external reviewers. Explain whether and if so what changes have been incorporated in the current proposal.

Main concerns/suggestions previously expressed by the external reviewers

Changes incorporated in the current proposal

13. Please indicate whether this application has previously been submitted to the Research Grants Council (RGC), i.e. a General Research Fund (GRF) application: (where appropriate)

- (i) Current application is a project independent of the GRF;
- (ii) Current application is a pilot study in preparation for the GRF;
- (iii) Current application forms part of the GRF and the application is seeking seed funding for the GRF;
- (iv) Current application serves to seek top-up funding for awarded GRF. *(please give the following project details)*

(a) Original Requested Amount of GRF Project:

(b) Approved Amount of GRF Project:

(c) Top-up Funding Sought for GRF Project (*this figure should NOT be greater than Item 11*):

14. Have you submitted any HKBU-endorsed RGC related schemes such as GRF / ECS / CRF / TBRS / AoE / HSSPFS / JRS-ANR / JRS-ESRC / JRS-NSFC / JRS-SRFDP / JRS-SFC (or equivalent) proposals as PI in the immediate past year? If no, please note the “Variable Quota for FRG Projects” to see whether you are eligible for FRG application.

Submission(s) in last academic year

Scheme	Ref No	Grant Title
GRF	12100317	The effect of sequential and simultaneous web-based interventions on the physical activity and fruit and vegetable intake of Chinese university students
JRS-GER	G-HKBU202/17	Evaluation of the Attractiveness of Urban Parks for Fitness-related Physical Activity among the Elderly: A Comparison Study in Hong Kong and Leipzig

15. Number of On-going FRG Projects held by the PI in the capacity of PI (Refer to the “Variable Quota System for FRG Projects”) (including those of which completion reports have not yet been submitted, where appropriate)

0

1 Project Code: FRG1/17-18/007

2 Project Code: _____

>2 Project Code: _____

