Physical activity (PA): The level of PA will be measured through the short Chinese version of the IPAQ questionnaire (Macfarlane et al., 2007). Participants will be asked to estimate the number of days and hours spent for vigorous, moderate and walking activities during the past week. **Fruit and vegetable intake (FVI):** FVI will be measured with four items, including fruit or vegetable juice, fruit, cooked or steamed vegetables, and raw vegetables (Rafferty et al., 2002). Respondents will be asked to count the number of portions of fruit and vegetables they consumed on average during a typical day. **Combined healthy lifestyle indicator:** In order to combine two behaviours, PA and FVI will be categorized according to whether or not the participants meet the health recommendations ([name], Fleig, Wiedemann, & Schwarzer, 2015). Based on the health guidelines for cardiac patients, the thresholds of 150 minutes PA per week (WHO, 2010) and 5 portions of fruit and vegetables (WHO, 2004) will be chosen. We use 1 and 0 to denote whether participants meet both recommendations or not.

2. Social-cognitive indicators of PA and FVI

Self-efficacy: Self-efficacy will be assessed with three dimensions consisting of motivational, maintenance and recovery self-efficacies with the stem "I am certain that..." followed by 5 items for PA such as "...I can be physically active permanently at a minimum of 5 days a week for 30 minutes even if it is difficult", or followed by 5 items for FVI such as "...I can eat 5 portions of fruit and vegetable a day even if it is difficult." (Cronbach's α for PA= .88; Cronbach's α for FVI= .92) (Luszczynska & Sutton, 2006). **Intention:** Intention for PA will be assessed with the stem "I intent to do for at least 30 minutes as day on minimum 5 days a week or at least 150 minutes a week with..." followed by 3 items such as "... vigorous sport", "...moderate PA" and "...mild PA". Intention for FVI will be measured by the stem "I seriously intend to..." followed by 3 items such as "eat at least 5 servings of fruit and vegetable each day"

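### The introduction to the physical activity items cues campus activity and names no work or home setting, which does not fit cardiac outpatients or the form's own walking item

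*Combined protocol and SAP*

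**What the plan says.** Section 6, Measures (Behaviour indicators), states: "The level of PA will be measured through the short Chinese version of the IPAQ questionnaire". No other PA measure is planned. These items supply the PA outcome under Objective 1. They also supply the PA half of the 0/1 healthy-lifestyle indicator, where the threshold is 150 minutes per week.

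The form itself is attached. In Part I, item 1, the introduction first announces an interest in "the kinds of physical activities that people do as part of their everyday lives". It then gives its only list of settings: "Please think about the activities you do at campus, such as, to get from place to place, and in your spare time". The vigorous block begins "Think about all the vigorous activities that you did in the last 7 days" and the moderate block "Think about all the moderate activities that you did in the last 7 days". Neither block names a setting. The walking block does: "This includes at work and at home, walking to travel from place to place".

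Section 6, Participants, restricts recruitment to one outpatient cardiac rehabilitation centre. Under "Please indicate your current work status", Part IV offers employment, pension and keeping house among its options. The next question asks whether the patient has returned to work.

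**The concern.** A campus is not a setting that these patients can be expected to have. For vigorous and moderate activity, the introduction is the only place where the form lists settings. It mentions neither the workplace nor the home, although Part IV shows that the investigators expect patients for whom one or both matter. A patient guided by that list may not think to report physical work or housework. Another may ignore a prompt that plainly does not apply and report everything. Two patients with the same week could then give different answers.

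What is at stake is the precision of the only PA measure and the correctness of a yes/no classification at 150 minutes. The Measures section states that threshold without limiting it to any setting. A cut-point is sensitive to omitted minutes for patients close to it. The questionnaires are completed online, and no interviewer is described who could correct a misreading.

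**Working it through.** The plan gives no figure on this point, so the check is a comparison of texts.

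| Place in the form (Part I, item 1) | Settings named | Scope |
|---|---|---|
| Opening sentence | None specific | "the kinds of physical activities that people do as part of their everyday lives" |
| Setting sentence | Campus, transport, spare time | A prompt to think about these; nothing is excluded |
| Vigorous item | None | "Think about all the vigorous activities that you did in the last 7 days" |
| Moderate item | None | "Think about all the moderate activities that you did in the last 7 days"; walking is expressly excluded |
| Walking item | Work, home, transport, recreation | "This includes at work and at home, walking to travel from place to place" |

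1. **Fit to the population.** Participants (Section 6) and Part IV describe adult outpatients who may be employed, retired or keeping house. Campus fits none of these descriptions. The sentence is wrong for the people who will read it.

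2. **Consistency within the form.** Work and home are named for walking, but not in the setting list that precedes vigorous and moderate activity. One instrument gives two different cues about scope.

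3. **Strength of the cue.** Where the form wants to restrict answers, it does so expressly: it limits vigorous and moderate activity to bouts of at least 10 minutes and keeps walking out of the moderate item. The setting sentence contains no such restriction. The vigorous examples, "vigorous physical activities like heavy lifting, digging, aerobics, or fast bicycling", include tasks that could be done at work or around a home. The text is a poor prompt, not a rule of exclusion.

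4. **Route to the outcomes.** Vigorous and moderate time is part of what the PA measure asks for, so any omission reaches the PA outcome and can reach the 150-minute classification. The Measures section gives no scoring rule. It does not say that the three activity types are summed, or whether walking counts towards 150 minutes.

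5. **Size.** To estimate under-reporting, one would need the share of vigorous and moderate activity done at work or at home and the share of patients who follow the setting list rather than the word all. The documents give neither, so no estimate can be computed.

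6. **Arms and waves.** The documents show a single questionnaire, with no wording specific to an arm or a wave. Nothing in them points to a difference in reporting between arms.

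**The case against.** The strongest reply is that the sentence does little harm. It follows an opening about everyday life, it excludes nothing, and the questions that patients answer ask for all vigorous and all moderate activity. Both arms see the same form. A patient who reads it the same way each time carries much the same omission through T1, T2 and T3, and the planned analysis is a repeated-measures comparison with time and group as factors. Section 6 also says that the electronic questionnaires were validated in a pilot with Chinese cardiac patients. The attached text is in English, and the deployed Chinese wording is not shown.

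Much of this stands, and it limits the point in four ways.

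- A reader might infer that patients are told to leave out work and household activity. The form does not say so.
- A reader might infer that the instrument drops work, house and yard from the standard questionnaire. The walking item includes work and home, and the source questionnaire is not reproduced, so only the absence of these words from one sentence can be shown.
- A reader might build a case such as 5 x 20 minutes of housework plus 2 x 30 minutes of exercise: 100 + 60 = 160 minutes, falling to 60 if the housework is left out, which moves the patient below 150. The arithmetic is right, but the case is invented. It assumes that no walking counts, and it sets aside the word all, under which a literal answer is 160.
- A patient who returns to work between waves changes activity in a setting that the sentence omits. The documents give no reason to expect this to differ between randomised arms.

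The validation statement does not remove the defect. No validation data are shown for the PA items, and the pilot wording is not given. The attached form also departs from the Measures section elsewhere. The PA intention stem is described there as 30 minutes on at least 5 days (150 minutes), but the form prints 20 minutes on at least 2 days (40 minutes). The printed text therefore cannot be assumed to be the text intended.

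**Conclusion.** The point holds as a minor defect. The setting sentence does not fit cardiac outpatients and is inconsistent with the walking item. It may lead some patients to under-report work or household activity in the vigorous and moderate items, which would add avoidable error to the PA outcome and to classification at 150 minutes per week. The documents do not support the stronger statement that the endpoint is measured in a student frame throughout, nor any claim of bias between arms. The size of the error is unknown.

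Two assumptions remain. The first is that the Chinese form carries the same sentence as the English text. The second is that vigorous and moderate minutes count towards the 150-minute criterion, which the plan implies but does not spell out. That the wording came from the team's earlier work with university students is plausible but an inference, and the conclusion does not depend on it.

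**What to change.** In the setting sentence, replace the campus reference with settings that suit these patients and match the walking item: at work, and in and around the home. Keep the existing transport and spare-time settings. The sentence then covers all three activity items with one scope. Use it unchanged at T1, T2 and T3, and check that the deployed Chinese form has the same wording.

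The Research Schedule already sets aside months 1-4 for refining the questionnaires, before recruitment begins in month 5. The change is one sentence in an electronic form and needs no extra patients, items or staff. It should be made before T1 opens, because a change between waves would break comparability over time.
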